## 2.2. App through a BYOD approach

The aim of this study is to determine the feasibility of using an app running on participants' own devices (i.e., through a BYOD approach) for the monitoring of depressive symptoms and mood-related constructs during pregnancy. We will assess the overall response rates of potential participants who are approached and asked to take part in this study. We will also compare two monitoring strategies, *retrospective* (using the EPDS) versus *retrospective plus momentary* (EPDS complemented with the EMA of mood, sleep, enjoyment, energy and worry), in terms of (1) drop-out rates, (2) adherence to sampling protocols, (3) patterns of engagement, (4) acceptance to participants, (5) timeliness of data collection, and (6) data completeness. We will assess if the implementation of a EMA technique affects the EPDS scores of participants allocated to the *retrospective plus momentary* condition. Additionally, we will assess if feedback by a member of the clinical care team affects engagement with the app, and participants' and clinicians' perceived usefulness of this approach.

### 2.2.1. Primary Objectives

- To determine the feasibility of using an app running on participants' own smartphones for the remote and longitudinal monitoring of depressive symptoms and mood-related constructs during pregnancy using retrospective assessment or a combination of retrospective and momentary assessment.

### 2.2.2. Secondary Objectives

- To assess differences in drop-out rates between the participants allocated to the retrospective assessment strategy (i.e., EPDS), and those allocated to the retrospective plus momentary assessment strategy (i.e., EPDS complemented with the EMA of mood, sleep, energy, enjoyment and worry).
- To assess differences in participants' adherence to sampling protocols between a retrospective assessment strategy (i.e., EPDS), and a retrospective plus momentary assessment strategy (i.e., EPDS complemented with the EMA of mood, sleep, energy, enjoyment and worry). We will achieve this by comparing the proportion of participants in each group that complete 100% of the expected assessments.
- To assess differences in usage patterns of the app between a retrospective assessment strategy and a retrospective plus momentary assessment strategy, including additional voluntary self-reporting, time spent using the app, number of interactions with other sections of the app, time to complete the self-assessments, and other ancillary usage data
- To assess differences in participants' acceptance of the app between a retrospective assessment strategy and a retrospective plus momentary assessment strategy through a post-study self-administered questionnaire

- To assess differences in timeliness of data collection between a retrospective assessment strategy and a retrospective plus momentary assessment strategy. We will achieve this by comparing the proportion of participants completing their assessments in response to a prompt displayed on their mobile devices between the two groups
- To assess differences in data completeness between a retrospective assessment strategy and a retrospective plus momentary assessment strategy. We will achieve this by comparing the proportion of complete records between the two groups
- To evaluate the impact of a momentary assessment technique of the EPDS scores by comparing the EPDS scores obtained at the start of the sampling period and the EPDS scores obtained at the end of this period. This will be assessed in the *retrospective plus momentary assessment* condition only
- To assess if feedback provided by a healthcare practitioner influences participants' and clinicians' engagement, acceptance and perceived usefulness of an app used for the remote and longitudinal monitoring of mood symptoms throughout pregnancy
- To describe the trend in EPDS scores and the variability in mood, sleep, energy, enjoyment and worry throughout the duration of this study
- To examine the correlation between variability in mood, sleep, energy, enjoyment and worry, and depressive symptoms (as assessed by the EPDS)
- To examine the association between contextual information and variability in mood, sleep, energy, enjoyment and worry, and the EPDS scores
- To assess safety and rates of adverse events due to the use of the app. Whilst these are expected to be non-existent or rare, our study provides a novel mode of depression screening, with potentially more frequent testing.

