### 3.3.1.2.7. Mean overall score on the EMA assessments

Mood, energy, enjoyment, sleep and worry will be assessed through a visual analogue scale (VAS) over-imposed on a 5-point Likert scale. For participants allocated to the retrospective plus momentary assessment condition, we will compute the overall score on each domain for each period of each assessment day.

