### 3.5.2.2.2. Retrospective plus momentary assessment

Participants in this condition will be required to complete a sampling period of 4 consecutive days once a month for 6 months; this period will be randomly selected from each calendar month, with no less than 2 weeks in between 2 consecutive sampling periods. The sampling period will start on day 1 with an administration of the EPDS and will conclude with another administration of the EPDS on day 4. In between (i.e., days 1 to 4 of the sampling period) participants will be asked to complete EMA assessments on mood, sleep, energy, enjoyment and worry plus 2 contextual information questions 3 times a day. The sampling hours will run between 10.00 and 22.00. This 12-hour window will be divided into 3 periods of 4 hours each, and with no less than one hour in between 2 consecutive assessments. Participants will receive a notification prompting them to complete the assessment at random times within each 4-hour period. Participants will have the option to accept or reject the request in the notification. Outside the sampling period, participants will be allowed to complete as many assessments as they wish to. During the sampling period however, participants will not be allowed to complete any additional assessments.

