## Appendix 6. Edinburgh Postnatal Depression Scale

As you are pregnant or have recently had a baby, we would like to know how you are feeling. Please check the answer that comes closest to how you have felt IN THE PAST 7 DAYS, not just how you feel today

In the past 7 days:

1. I have been able to laugh and see the funny side of things
  - As much as I always could
  - Not quite so much now
  - Definitely not so much now
  - Not at all
2. I have looked forward with enjoyment to things
  - As much as I ever did
  - Rather less than I used to
  - Definitely less than I used to
  - Hardly at all
3. I have blamed myself unnecessarily when things went wrong
  - Yes, most of the time
  - Yes, some of the time
  - Not very often
  - No, never
4. I have been anxious or worried for no good reason
  - No, not at all
  - Hardly ever
  - Yes, sometimes
  - Yes, very often
5. I have felt scared or panicky for no very good reason
  - Yes, quite a lot
  - Yes, sometimes
  - No, not much
  - No, not at all
6. Things have been getting on top of me
  - Yes, most of the time I haven't been able to cope at all
  - Yes, sometimes I haven't been coping as well as usual
  - No, most of the time I have coped quite well
  - No, I have been coping as well as ever
7. I have been so unhappy that I have had difficulty sleeping
  - Yes, most of the time
  - Yes, sometimes
  - Not very often
  - No, not at all
8. I have felt sad or miserable
  - Yes, most of the time
  - Yes, quite often
  - Not very often
  - No, not at all

9. I have been so unhappy that I have been crying

- Yes, most of the time
- Yes, quite often
- Only occasionally
- No, never

10. The thought of harming myself has occurred to me

- Yes, quite often
- Sometimes
- Hardly ever
- Never

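### The correlation of EMA variability with EPDS has no stated analysis; on bounded scales an unadjusted within-woman SD can track EPDS through mean level alone

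*Combined protocol and SAP*

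**What the plan says.** The objective, in section 2.2.2, is "To examine the correlation between variability in mood, sleep, energy, enjoyment and worry, and depressive symptoms (as assessed by the EPDS". A companion objective relates contextual information to the same variability and to EPDS scores.

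Each of the five domains "will be assessed through a visual analogue scale (VAS) over-imposed on a 5-point Likert scale" (section 3.3.1.2.7), with the response options in Appendix 2. The only EMA summary defined there is a score: "we will compute the overall score on each domain for each period of each assessment day". No variability measure is defined anywhere.

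Section 3.5.2.2.2 sets "a sampling period of 4 consecutive days once a month for 6 months", with the EMA items "plus 2 contextual information questions 3 times a day". Each period opens with an EPDS on day 1 and "will conclude with another administration of the EPDS on day 4". The EPDS asks "how you have felt IN THE PAST 7 DAYS, not just how you feel today" (Appendix 6).

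Section 3.8.2 runs from the positive predictive value to timeliness of data collection. It contains no entry for this objective.

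**The concern.** On a scale with fixed ends, the spread of a woman's scores is squeezed when her mean is near an end and has more room as the mean moves inward. Table 3 excludes women with a diagnosed, treated or recent common mental health disorder, so mood and worry may well sit toward the good end, although the documents do not show this. If women with worse average mood or worry also have higher EPDS scores, their SDs will be larger for a mechanical reason. A raw correlation of SD with EPDS then partly restates that worse average mood goes with more depressive symptoms.

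The study asks what momentary assessment adds to the EPDS, and section 6.5 says its findings will inform later trials. Reporting instability as a marker of depressive symptoms when only the average level is related would mislead that work.

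There is a second, separate gap. The plan does not say which of the two EPDS scores in a period is paired with the EMA data, and their recall weeks overlap the EMA days very differently.

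**Working it through.** **The plan's own figure.** Section 3.6 gives 96 per BYOD arm for a 95% interval of 10 on an adherence rate. Reading this as ±10 percentage points and taking p = 0.5: n = 1.96² × 0.25 / 0.10² = 96.04, which agrees. That number was not set for this correlation, but only the momentary arm has EMA data, so N = 96 is used below.

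**Prompts.** 4 days × 3 per day = 12 per period; 12 × 6 = 72 per woman.

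**Smallest significant correlation.** With Fisher's z, tanh(1.96/√93) = 0.20. A raw r of about 0.2 would therefore be declared significant.

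**Why the bound matters.** On a 1-5 scale a woman with mean m cannot have an SD above √((m − 1)(5 − m)). At m = 1.1 this is √(0.1 × 3.9) = 0.62; at m = 3 it is √(2 × 2) = 2.

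**Simulation on a 1-5 scale (1 = best).** Assumptions not in the documents: between-woman SD 0.7; typical within-woman SD 0.8, varying between women (log-SD 0.25) independently of depression; ρ is the correlation of depression with EMA level. Scores are limited to 1-5 and kept continuous; 12 prompts, one period, 800 replicates. Adjustment removes the woman's EMA mean and its square.

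| Mean level | ρ = 0.3: raw r, false positives | adjusted | ρ = 0.6: raw r, false positives | adjusted |
|---|---|---|---|---|
| 1.5 | 0.18, 44% | 6% | 0.37, 97% | 8% |
| 2.0 | 0.13, 24% | 5% | 0.26, 74% | 6% |
| 2.5 | 0.06, 8% | 4% | 0.13, 25% | 7% |
| 3.0 | about 0, 5% | 5% | about 0, 6% | 4% |

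Averaging the SD over six periods at mean 2.0 gives raw r of 0.16 and 0.32, with 35% and 88% false positives. Rounding to Likert points changes little. With ρ = 0, or with no bounds, r is about 0 and the rate is 4% to 7%.

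**Simulation on a 0-100 scale.** (Mean, between-SD, within-SD) = (20, 18, 15), (30, 20, 15), (30, 20, 10); level-EPDS correlation 0.4 or 0.6; 1,000 replicates.
- Identical true SDs: raw r 0.18 to 0.39. False positives are about 50% to 98% with a within-woman SD of 15, falling to the mid-40s at the low end when it is 10. After adjustment r is 0.01 to 0.03, with 4% to 7% false positives.
- True SDs varying with log-SD 0.4 (e^±0.4, so roughly 0.67 to 1.49 times typical at one SD): raw r 0.11 to 0.26, false positives about 20% to 75%.
- Mean 50: 5% to 7%. Mean 65: r about −0.05 to −0.20, so the sign reverses.

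**Recall window.** The day-1 EPDS looks back over a week that shares at most one day with the EMA days. The day-4 EPDS covers all four, plus about three earlier days. In a separate simulation without bounds (2,000 replicates) and with no true link, r was about 0 and the false-positive rate was 5.3% (day-1) and 4.3% (day-4). With a true link, r was 0.60 against the day-4 EPDS and 0.32 against the day-1 EPDS.

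**The case against.** The strongest reply is that the plan is silent rather than wrong. It says only that a correlation will be examined; a reader might infer a commitment to a raw, per-period SD, but the text does not make one. The preceding objective describes variability over the whole study, so even the period is open. This stands: the documented gap is an undefined analysis. The unadjusted correlation is nevertheless the plain reading of the objective, and it is the one that can mislead.

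Four other inferences go further than the documents allow.
- That the recall mismatch can produce a false correlation. It cannot; it only dilutes a true one.
- That section 3.3.1.2.6 averages each woman's day-1 and day-4 EPDS for this purpose. That section describes group means, overall and by month, and nothing links it to the correlation.
- That a false finding is nearly certain. The highest rates need means close to a bound and a strong level-EPDS correlation, and on the 0-100 scale identical true SDs as well.
- That all five domains cluster at the healthy end. The exclusions concern depression and anxiety; they say little about how rested or energetic pregnant women feel. Those means could lie mid-scale, where the artefact vanishes, or beyond it, where it reverses.

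Finally, the objective is secondary in a feasibility study. It has no stated hypothesis, no sample size of its own and no decision attached. That limits the severity but does not remove the point.

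**Conclusion.** The point holds in a limited form. Nothing in the plan protects the variability-EPDS correlation from the link between SD and mean on a bounded scale. With N = 96 and means toward one end, that link can produce raw correlations around the 0.20 needed for significance, or above it, when instability has no relation to depression. The false-positive ranges are conditional on assumed EMA means, spreads and level-EPDS correlations, none of which the documents give; the artefact is absent at mid-scale and may differ in size and sign between domains. In every setting checked, adjusting for mean and mean squared brought false positives close to 5% (4% to 8%). The unspecified EPDS occasion is a separate weakness that costs strength of association, not validity under the null. This is a lower-severity improvement to an exploratory secondary objective.

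**What to change.** Add an entry to section 3.8.2 stating that:
- the within-woman SD is computed per domain and sampling period;
- it is related to the day-4 EPDS of the same period, adjusted for the woman's mean EMA score in that period (linear and squared);
- there is one model per domain, pooling the six periods with a random effect for woman, which gives five associations instead of 6 × 5 = 30 separate ones and respects the repeated periods;
- the association of mean level with EPDS is shown first, so that any added value of variability is visible;
- the analysis is repeated with the day-1 EPDS as a sensitivity analysis.

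The simulations tested the adjustment with one row per woman (one period, or the SD averaged over six), not the pooled random-effect model itself.

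The cost is wording only, since all the data are already collected. The downside is that the adjusted association will usually be smaller than the raw one.

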### 3.3.1.2.2. Drop-out rates

The proportion of participants who stop completing the retrospective or the retrospective plus momentary assessments before the end of the study (i.e., before 6 months). For those participants taking part in the app through a BYOD approach, we will consider they have dropped out if they miss 2 consecutive assessments. In this case, a notification on their phones will ask them to complete a question about the reason for not completing the assessments.

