### 3.3.1.2.3. Adherence to sampling protocols

The proportion of participants who complete 100% of the expected assessments over the duration of the study.

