### 3.4.2. Software

For the study using tablet computers in antenatal clinics, we will use SNAP Surveys to create the app versions of the (i) personal demographic information survey questionnaire, (ii) the Whooley questions, and (iii) the EPDS.

For the study using an app through a BYOD approach, we will use SNAP Surveys to present the (i) informed consent form [*mHealth for the EMA of mood during pregnancy – Informed Consent Form, Version 1.2, dated 19 January 2017*], (ii) the personal demographic information survey questionnaire, (iii) the Whooley questions, and (iv) the EPDS. In addition, we will use a bespoke app developed by [name] to collect (i) the EPDS, (ii) EMA assessments, (iii) the Contextual Information survey, and (iv) the post-study survey. This app will also include additional features providing additional information about mood during pregnancy and a list of available resources.

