### 3.5.2.2.1. Retrospective assessment

Participants in this condition will be asked to complete the EPDS once a month for 6 months. The day on which participants are required to complete the EPDS will be selected at random from each calendar month, and with no less than 2 weeks in between 2 consecutive sampling periods. On that day, we will select a random time between 10.00 and 22.00 to administer the EPDS. At that time, a notification will be displayed on a participant's phone asking her to complete the EPDS. They will then be able to accept the request or reject it. Outside the sampling period, participants will be allowed to complete as many assessments as they wish to. However, during the sampling period, participants will not be allowed to complete any additional assessments.

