### 3.5.2.2.3. Duty of care

The EPDS is a screening tool that indicates the likely risk of depression during pregnancy or postpartum. Scores between 10 and 12 points indicate an increased risk of depression; whereas a score of 13 points or more indicates that the diagnostic criteria for major depression have probably been met. In both cases, further assessment is warranted to confirm a diagnosis of depression. In addition, question 10 of the EPDS deals with a woman's risk of self harm. Scores of between 1 and 3 points on this question warrant further assessment.

For every participant, we will collect at baseline the following contact details:

- GP: telephone number, email address and postal address
- Designated clinician: telephone number, email address and postal address

The system will send an email notification to the study coordinator if any participant:

- Scores 10 points or more on the EPDS
- Scores 1 point or more on Question 10 of the EPDS regardless of her overall score on the EPDS
- Completes more than 2 instances of the EPDS in one day

Upon receiving any notification, the study coordinator will notify the participant's risk to all of her contacts via the telephone. This will be followed up by a written notification using the documents *Antenatal mental health screening – Letter to the GP (Version 1.1, dated 06 December 2015)* or *Antenatal mental health screening – Communicating results to the clinician (Version 1.0, dated 28 April 2015)* being posted to the participant's GP and her designated clinician. The study coordinator will action this within 24 hours.

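### The app study's safety objective has no adverse-event definition, no systematic collection and no analysis, and duty-of-care alerts are not counted although one arm has twice the scheduled EPDS

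*Combined protocol and SAP*

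**What the plan says.** Section 2.2.2 sets the objective "To assess safety and rates of adverse events due to the use of the app". It expects such events to be absent or rare, and gives as its reason that "our study provides a novel mode of depression screening, with potentially more frequent testing".

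The seven app-study endpoints (3.3.1.2.1 to 3.3.1.2.7) are response, drop-out, adherence, timeliness, completeness, mean EPDS and mean EMA scores. Adherence, for example, is "The proportion of participants who complete 100% of the expected assessments over the duration of the study". According to section 3.4.2, the bespoke app collects "i) the EPDS, (ii) EMA assessments, (iii) the Contextual Information survey, and (iv) the post-study survey". The analyses specific to the app study (3.8.2.8 to 3.8.2.10) cover drop-out, adherence and timeliness.

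The schedules differ by arm. In the retrospective arm (3.5.2.2.1), "Participants in this condition will be asked to complete the EPDS once a month for 6 months". In the retrospective plus momentary arm (3.5.2.2.2), each monthly sampling period "will start on day 1 with an administration of the EPDS and will conclude with another administration of the EPDS on day 4". Both arms may complete further assessments at will outside sampling periods.

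Under section 3.5.2.2.3, "The system will send an email notification to the study coordinator if any participant" meets one of three triggers: an EPDS total of 10 or more, an item 10 score of 1 or more, or more than 2 EPDS in a day. The coordinator then telephones all the woman's listed contacts and follows up in writing.

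**The concern.** An objective about rates needs a numerator, a denominator and a rule for what counts. None of these is given. A report that mentions no adverse events could then be taken to confirm the stated expectation, when women were never asked about harm in any planned way.

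The alerts are the most direct consequence of more frequent testing that the study generates. Each brings work for the coordinator, the GP and the designated clinician, which bears on the primary feasibility objective in section 2.2.1. Because one arm is scheduled for twice as many EPDS, alerts would differ between arms through opportunity alone, and the plan provides neither the count nor a like-for-like comparison.

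**Working it through.** **1. Is there any route from objective to result?**

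- Definition of an adverse event, or of how it is attributed to the app: none found.
- Endpoint: none among the seven in 3.3.1.2.
- Instrument: the EMA items, contextual questions, participant post-study survey and supporter survey (Appendices 2, 3, 4 and 7) contain no question on harm or distress from using the app.
- Analysis: none in 3.8. The table of contents lists no safety-reporting section, so removed text does not explain the gap.

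The nearest outputs are:

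- Section 3.8.1: proportions by group in EPDS bands 0–9, 10–12 and 13 or above, and scoring 2 or 3 on item 10. No time point is given. The item 10 threshold differs from that of the alert (1 or more), and the repeated-use trigger is absent.
- Section 3.3.1.2.2: after 2 consecutive missed assessments, "a notification on their phones will ask them to complete a question about the reason for not completing the assessments".
- Appendix 4: open questions on what was liked least and on other comments, and a rating of how often reports were requested.

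**2. The plan's own sample size, and what it could say about harm**

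Section 3.6 gives 96 per arm, sized on adherence. Reading the interval of 10 as ±10 points and assuming a proportion of 0.5: 1.96² × 0.25 / 0.10² = 96.04, so 96 is reproduced.

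If harm were collected and no events were seen in n women, the exact two-sided 95% upper limit is 1 − 0.025^(1/n):

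- n = 96: 3.8%
- n = 192: 1.9%

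Without systematic collection, no such limit can be claimed.

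**3. Scheduled EPDS by arm**

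- Retrospective: 1 × 6 = 6 in the app.
- Momentary: 2 × 6 = 12 in the app, a ratio of 2.0.
- Adding the one baseline tablet EPDS in each arm (3.5.2.2): 7 against 13, a ratio of 1.86.

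**4. Illustration of unequal alert opportunity (trigger 1 only)**

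Assumptions: full completion; the same chance p of an EPDS of 10 or more at every administration in both arms; p = 12%. The 12% is the depression prevalence in section 3.6, borrowed for illustration. It is not a stated alert rate.

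Expected positives per 96 women, whatever the within-woman correlation:

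- Retrospective: 96 × 6 × 0.12 = 69
- Momentary: 96 × 12 × 0.12 = 138

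The chance of at least one positive in m administrations, with within-woman correlation ρ, is taken from a beta-binomial: 1 − B(a, b + m)/B(a, b), where a = p(1 − ρ)/ρ and b = (1 − p)(1 − ρ)/ρ. At ρ = 0.5, for example, a = 0.12 and b = 0.88.

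| p | ρ | m = 6 | m = 12 |
|---|---|---|---|
| 12% | 0.3 | 34% | 44% |
| 12% | 0.5 | 26% | 32% |
| 12% | 0.7 | 20% | 23% |
| 12% | 0.9 | 14.5% | 15.3% |
| 7.4% | 0.5 | 17% | 21% |
| 7.4% | 0.7 | 13% | 15% |

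The 7.4% is the first-trimester prevalence in section 1, relevant because app-study women enter in the first trimester (3.2.1).

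**The case against.** The strongest reply is that this is a feasibility study with a secondary safety objective, that events are expected to be rare, and that the plan is not blind to harm. Section 3.8.1 reports EPDS bands and item 10 scores by group, section 2.2.2 compares voluntary self-reporting between arms, and the missed-assessment question and open comments could reveal distress. This stands in part: a reader might infer that nothing relevant is collected, or that alerts leave no trace in the results, and the documents do not support either. What remains is that none of these outputs is systematic, counts alerts, or yields an adverse-event rate.

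Other stronger readings also fail:

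- **Alerts are adverse events.** An alert marks symptoms or repeated use that the system detected. It is not an event caused by the app, so counting alerts would not meet the objective.
- **The gap in women alerted could be about 25 points.** Independence at 12% gives 1 − 0.88^6 = 54% against 1 − 0.88^12 = 78%. But the paired EPDS fall on days 1 and 4 of one period and each looks back 7 days, so independence is implausible.
- **Cost of wrongly identified women is the main case against screening.** Section 1 cites it from one cost-effectiveness analysis. The national screening committee's three reasons are different. Alert counts could not show who was wrongly identified anyway, because the app study has no diagnostic reference standard.
- **Alert-led contact changes later EPDS scores.** It may, but nothing in the documents shows it.

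**Conclusion.** The point holds as a gap between objective and means: the safety objective cannot be answered by the plan as written, and the shortfall cannot be repaired at analysis. It should be corrected, though it does not affect the study's primary objective or sample size.

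The absence of a definition, collection and analysis rests on the text alone. The doubling of scheduled in-app EPDS is exact. The doubling of expected positives assumes equal risk and full completion; voluntary EPDS could move actual exposure away from 2:1. The gap in women with at least one positive is illustrative: about 10 points at correlation 0.3, under 1 point at 0.9, and smaller at a prevalence of 7.4%. The burden argument therefore lies more in the number of alerts than in the number of women alerted.

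**What to change.** 1. **Adverse events.** Add to 3.3.1.2 and 3.8 a short definition of an app-related adverse event, including how relation to the app is judged. Collect it with one distress or harm item in the app during follow-up, the same item within the drop-out question of 3.3.1.2.2, and one item in Appendix 4. The survey item alone would miss women who stop early. Report rates by arm with exact 95% confidence intervals.
2. **Alerts, as a feasibility and burden outcome and not as adverse events.** Tabulate by arm and trigger, per woman and per completed EPDS, first for all EPDS (the burden of each strategy) and then for the first scheduled EPDS of each month only (the like-for-like comparison).
3. **Item 10.** Reconcile for reporting the thresholds in 3.5.2.2.3 (1 or more) and 3.8.1 (2 or 3). This review does not say which is right.
4. **Alternative.** If harm is not to be collected, withdraw the objective.

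Splitting the EPDS trend by prior alert is tempting but should not be added: it selects on a high earlier score, so regression to the mean would shape the result.

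The cost is one or two short items, some SAP wording and a little tabulation. The protocol describes an alert email, not an alert log, but score-based alerts can be rebuilt from stored EPDS scores; the repeated-use trigger also needs completion dates to be kept. The duty-of-care procedure is unchanged.
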